## **6.2 Subject Disposition**

Disposition will be summarized for Part I, Part II, Parts III/IV, and the study overall.

For Part I, the number of subjects who were screened, were screen failures, were randomized to treatment, included in the Safety, ITT and PP, completed Part I (i.e., attended Week 16 visit) and prematurely discontinued from the study during Part I (along with the reasons for discontinuation), as well as found to be non-responders and randomized to be discontinued after Part I will be presented. Additionally, if subject eligible to continue to Part II discontinues the study right after completion of Part I without being re-randomized for Part II, such subjects will also be summarized by reason for discontinuation.

For Part II, the summary will include the subjects who were re-randomized for Part II. It will present the number and percentage of subjects who were re-randomized to continue in Part II, completed Part II (i.e., attended Week 28 visit) and prematurely discontinued from the study during Part II (along with the reasons for discontinuation) as well as found to be non-responders and discontinued after Part II. Additionally, if a subject who is eligible to continue to Part III discontinues the study right after completion of Part II without receiving any study drug in Part III, such subjects will also be summarized by reason for discontinuation.

For Parts III/IV, the summary will include the subjects who were eligible to continue to Part III at Visit 16. It will present the number and percentage of subjects who were eligible to continue in Part III, completed Part III (i.e., attended Week 52 visit) and prematurely discontinued from the study during Part III (along with the reasons for discontinuation) and separately prematurely discontinued from the study during Part IV (along with the reasons for discontinuation).

For the study overall, the summary will present the number of subjects who were screened, were screen failures, were randomized to treatment, included in the Safety, ITT, and PP, attended the visits at Weeks 16, 28, 52 and 54, completed the study and prematurely discontinued from the study at any time (along with the reasons for discontinuation).

All disposition information will be listed. Also, a listing of enrollment details will provide the date of informed consent and inclusion/exclusion criteria not met, if any.

## **6.3 Demographic and Baseline Characteristics**

Demographic and baseline characteristics will include:

- age
- sex
- race

- ethnicity
- baseline height, weight, and body mass index (BMI)
- time since psoriasis diagnosis (years)
- whether the subject took any prior biologic therapy for psoriasis
- whether the subject has scalp, palmoplantar, nail psoriasis or psoriatic arthritis (PsA) or other types of psoriasis.
- whether the subject meets Classification of Psoriatic Arthritis (CASPAR) criteria
- Baseline PASI score
- Baseline BSA affected %
- Baseline IGA

Descriptive statistics will be presented for continuous variables. Frequency counts and percentage will be presented for categorical variables. Height will be presented in centimeters, weight in kilograms and BMI in kg/m^2.

Age will be derived from Informed Consent Date and Date of Birth as the number of whole years between those two dates.

These analyses will be performed for the ITT population.

All demographic parameters and baseline characteristics will be presented in the by-subject listings.

#### **6.4 Medical History**

Medical history will be summarized by Medical Dictionary of Regulatory Activities (MedDRA), Version 25.0, System Organ Class and Preferred Term. One subject will be counted once for each applicable Preferred Term and System Organ Class. This summary will be performed for the ITT population. All medical history information will be listed.

#### **6.5 Ophthalmological History**

Number and percentage of subjects with each finding of past ocular history and each type of ocular surgery as collected at the Ophthalmological History eCRF will be presented by treatment group.

All ophthalmological history conditions and surgeries will be listed.

#### **6.6 Protocol Deviations**

Protocol deviations will be derived algorithmically as well as reported by sites. A subset of protocol deviation will be classified as affecting proper administration of the treatment or accurate evaluation of its effectiveness and thus excluding from the PP population. Specific deviation, their exclusion status and rules for their algorithmic detection are defined in the separate Protocol Deviations Specification document.

All reasons for exclusion from the PP population will be summarized by reason category and treatment group and listed. This analysis will be performed for the ITT population. The final

determination of which protocol deviations exclude subjects from the PP population will be made by the sponsor during the blinded data review prior to the database lock.

## 6.7 CASPAR Criteria

All subjects with a medical history of PsA reported at the screening or baseline will be assessed to establish if there is a diagnosis of PsA per the CASPAR criteria. The diagnosis of PsA will be done by a rheumatologist or an orthopedist, or a qualified trained designee (not applicable at sites where an independent assessor experienced in performing joint assessments is not available). According to CASPAR, the establishment of the diagnosis of PsA requires the presence of inflammatory joint disease (peripheral, axial or enthesitis) with at least three points from the following features: evidence of skin psoriasis (current psoriasis was assigned a score of 2, while history of psoriasis or familial history of psoriasis were assigned a score of 1 each, as were all the other features), psoriatic nail dystrophy, rheumatoid factor negativity, dactylitis, and characteristic radiological evidence.

Results from CASPAR criteria evaluation will be listed.

### 6.7.1 Study Drug Exposure and Compliance

Duration of exposure will be defined separately for each treatment group, by study part (Part I and Parts II/III) and overall. Duration of exposure in each study part will be calculated as [REDACTED]

[REDACTED] The date of the last dose in the study will be collected at the End of Study eCRF. For subjects staying on the same dose throughout the study, total duration of exposure in the study will be defined as the sum of their durations of exposure in Part I and Part II/III.

Total dose of SCD-044 will be calculated based on the number of tablets taken as collected at the Study Product Accountability eCRF. The strength of each tablet will be assumed to follow the protocol-defined [REDACTED] schedule. Average daily dose of SCD-044 will be calculated as Total dose taken / Duration of Exposure.

Compliance will be calculated for maintenance periods only and separately for Part I and Parts II/III as [Total number of tablets of any strength taken] / [Planned number of tablets] \*100%.

Planned number of tablets will be defined as follows:

- For Part I maintenance period:

○ [REDACTED]  
[REDACTED] - [REDACTED]  
[REDACTED] - [REDACTED]  
[REDACTED] - [REDACTED]

- For Part II/III maintenance period:

○ [REDACTED]  
[REDACTED] - [REDACTED]

○

Date of discontinuation will be defined as the date of early termination visit, if one occurred, otherwise the discontinuation date collected on the End of Study eCRF.

If Total number of tablets of any strength taken cannot be determined, the compliance will be missing.

Compliance in the maintenance periods will be classified as <75%, 75%-125% and >125%. Subjects with compliance <75% or >125% will be considered non-compliant with the study medication.

Duration of exposure, average daily dose and compliance will be summarized descriptively by treatment group for the Safety population.

Number and percentage of subjects who underwent re-[REDACTED] will be presented separately for Part I and Parts II/III by treatment group for the Safety population. Number of missed doses in the [REDACTED] period will be summarized descriptively separately for Part I and Parts II/III by treatment group for the Safety population.

## 6.8 Efficacy Analyses

### 6.8.1 Imputation of the primary and key secondary endpoints

All subjects in the ITT population with the following intercurrent events prior to Week 16 will be imputed as non-responders for both the primary endpoint and key secondary endpoint.

- taking prohibited medications prior to Week 16
- discontinuing from the study due to lack of efficacy, protocol deviation or AE prior to Week 16

Subjects who did not have intercurrent events prior to Week 16, and either do not have a Week 16 PASI assessment or do not have a PASI baseline will be referred to as “subjects missing at random” for the primary endpoint. Similarly, subjects who did not have intercurrent events prior to Week 16, and either do not have a Week 16 IGA assessment or do not have an IGA baseline will be referred to as “subjects missing at random” for the key secondary endpoint.

The PASI values of these subjects will be imputed using multiple imputations (MI) approach under the “missing at random” (MAR) assumption. For each subject who is “missing at random” in the ITT population 50 imputations will be performed using Fully Conditional Specifications (FCS) regression imputation model with the factors for gender, prior biologic therapy (Yes/No), PASI score at baseline and weeks 4, 8, 12 and 16. All subjects in the ITT population will be used in the model. Imputed PASI scores will be rounded to 1 decimal place and restricted to the range 0 to 72. For all imputed record PASI75 response will be calculated based on the imputed PASI value using the regular PASI75 definition, i.e. 75% reduction from baseline in the PASI score. See section 11.4.1 for sample SAS code.

The key secondary endpoint values (i.e. the binary outcomes of whether the subject achieved the IGA response or not) will also be imputed using multiple imputations (MI) approach under the “missing at random” (MAR) assumption. For each subject who is “missing at random” in

the ITT population 50 imputations will be performed using Fully Conditional Specifications (FCS) logistic regression imputation model with the factors for gender, prior biologic therapy (Yes/No), IGA grades at baseline and weeks 4, 8, and 12. All subjects in the ITT population will be used in the model. See section 11.4.2 for sample SAS code.

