- **Part IV:** Week 52 to Week 56; After Week 52 (or early termination of study treatment prior to Week 52), the study treatment will be stopped, and all subjects will enter the follow-up period to monitor safety and tolerability for 4 weeks following the last dose of study treatment. During the follow-up period, subjects should continue study approved concomitant medications only. However, they may be placed on appropriate therapies for safety concerns or significant worsening of psoriasis based on the judgment of the Investigator.

Clinical evaluations will be performed at:

[REDACTED]

On-site Visit 1: Screening Visit (Week \geq -4 / Day -28 to -1);
On-site Visit 2: Baseline Visit (Week 0 / Day 1; before 12 noon);
On-site Visit 7: [REDACTED]
On-site Visit 8: [REDACTED]
On-site Visit 9: [REDACTED]
On-site Visit 10: [REDACTED]
On-site Visit 14: [REDACTED]
On-site Visit 15: [REDACTED]
On-site Visit 16: [REDACTED]
On-site Visit 17: [REDACTED]
On-site Visit 18: [REDACTED]
On-site Visit 19: End of treatment visit (Week 52 / Day 365 \pm 3 Days; before 12 noon);
On-site Visit 20: Follow-up visit (Week 56 / Day 393 \pm 3 Days);

Phone or in person contacts may be scheduled [REDACTED]

[REDACTED] to collect information on concomitant medication, compliance with the study drug use, health changes (AEs & AESI), queries for PML and PRES and to provide instructions.

Subjects will be admitted into the study after informed consent has been obtained. An Unscheduled Visit is allowed at any time, for any reason, if in the Principal Investigator's opinion it is warranted. If a subject is discontinued from the study during an Unscheduled Visit, the Unscheduled Visit will be referred to as an Early Discontinuation Visit and all procedures scheduled for Early Discontinuation will be performed. If the Unscheduled Visit is not an Early Discontinuation Visit (i.e., the subject will continue to take part in the study), then all procedures scheduled for that Unscheduled Visit will be performed. Subjects who are discontinued early from the study must attend the Follow-up visit 4 weeks after the date of Early Discontinuation.

Study Population:

Key Inclusion Criteria

1. Males and non-pregnant non-lactating females \geq 18 years of age providing written informed consent prior to any study-related procedures.
2. Diagnosis of predominantly plaque psoriasis for \geq 6 months as determined by subject interview and confirmation of diagnosis through physical examination by Investigator

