4.7 Subject Disposition and Discontinuation

Investigators are urged to enroll only those eligible Subjects who are likely to complete the entire study and who are willing to comply with the protocol-specified procedures. It is the right and duty of the Investigator to interrupt the treatment of any Subject whose health or well-being may be threatened by continuation in this study, or who may be experiencing unmanageable factors that may interfere with the study procedures and/or the interpretation of study results. Such Subjects should be withdrawn from the study rather than continued under a modified regimen.

Subjects will be removed from the study for any of the following reasons:

- If the Subject withdraws his or her consent for any reason; (note: if reason of discontinuation is due to COVID 19 related reasons this is to be noted.)
- If the Subject's condition has worsened to the degree that the Principal Investigator feels it is unsafe for the Subject to continue in the study;
- If the Subject's drug code is unblinded (on a case-by-case basis in consultation with the MM);
- If an adverse event occurs for which the Subject desires to discontinue treatment or the Principal Investigator determines that it is in the Subject's best interest to be discontinued;
- If there is a significant protocol violation;
- If the Subject is lost to follow-up;
- If the Subject becomes pregnant;
- If the Subject becomes a prisoner or become involuntarily incarcerated;
- Any other reason that may affect the outcome of the study or the safety of Subjects
- Termination of the study by the IRB; or
- Termination of the study by the Sponsor.

Additional reasons for Subjects to be removed from the study:

- Diagnosis of new onset of a Malignancy
- Diagnosis of Cryptococcal central nervous system (CNS) infection.
- Diagnosis of Progressive multifocal leukoencephalopathy (PML)
- Diagnosis of Posterior reversible encephalopathy syndrome (PRES)
- [REDACTED]
- On a case-by-case basis in consultation with independent MM in case of use of prohibited medications
- Clinically significant abnormalities that put the subject safety at risk if continued in the study including but not limited to
 - [REDACTED]
 - [REDACTED]
 - [REDACTED]
 - [REDACTED]
 - [REDACTED]
 - [REDACTED]

- [REDACTED]
- [REDACTED]
- [REDACTED]
- [REDACTED]
- [REDACTED]
- [REDACTED]

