6.3 Pharmacodynamic (PD) biomarkers

[REDACTED] a blood sample will be collected for testing of:

- Cytokines in plasma/serum: [REDACTED]
- Cell types in blood:
 - [REDACTED]
 - [REDACTED]
 - [REDACTED]
 - [REDACTED]
 - [REDACTED]
 - [REDACTED]

Additional biomarkers may be included during the study.

[REDACTED]

Subjects who are withdrawn permanently from study drug but remain in the study should not have any more PD biomarker samples taken.

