### 2.2 Primary Estimand

The primary estimand is defined as follows:

Population of interest	Subjects with moderate to severe plaque psoriasis
Outcome Measure/Endpoint	Achieving at least 75% improvement in PASI at Week 16
Treatment	SCD-044 [REDACTED] and placebo once daily
Intercurrent Event	

Use of prohibited medications (as determined during blinded data review)

Early treatment discontinuation due to lack of efficacy, protocol deviation or AEs

 
Composite strategy will be applied to these intercurrent events and the subjects with intercurrent events will be treated as non-responders.

Population-level Summary Measure	Difference in proportions between each the active treatment arms and placebo arm

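### The estimands count stopping treatment for three listed reasons as non-response, but SAP 6.8.1 applies non-responder imputation only to leaving the study for those reasons

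*SAP*

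**What the plan says.** **Estimand.** SAP 2.2 lists two intercurrent events. One is use of prohibited medication. The other is "Early treatment discontinuation due to lack of efficacy, protocol deviation or AEs". The strategy is stated in the same table: "Composite strategy will be applied to these intercurrent events and the subjects with intercurrent events will be treated as non-responders". SAP 2.4 repeats both events and the strategy for the IGA endpoint.

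**Implementation.** SAP 6.8.1 begins: "All subjects in the ITT population with the following intercurrent events prior to Week 16 will be imputed as non-responders". Two bullets follow. The second reads "discontinuing from the study due to lack of efficacy, protocol deviation or AE prior to Week 16". The next paragraph defines the group sent to multiple imputation: "Subjects who did not have intercurrent events prior to Week 16, and either do not have a Week 16 PASI assessment", or who lack a baseline value. The IGA endpoint is handled in the same way. SAP 6.1.3 adds no definition and points to 6.8.1.

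**Protocol.** Section 6.3 contains an instruction for subjects who are off drug but still in the trial: "Subjects who are withdrawn permanently from study drug but remain in the study should not have any more PD biomarker samples taken". Section 4.7 lists reasons for removal from the study, one of which starts: "If an adverse event occurs for which the Subject desires to discontinue treatment or the Principal Investigator determines". The synopsis, under Part IV, says "After Week 52 (or early termination of study treatment prior to Week 52), the study treatment will be stopped", and such subjects then enter a four-week follow-up.

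**The concern.** The reasons are the same in both SAP sections, but the event is not: one stops treatment, the other leaves the study. Programmers will code 6.8.1. Nothing in the available text says that stopping treatment counts as leaving the study, and Protocol 6.3 treats them as separable.

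Two kinds of subject fall between the definitions:

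- one who stops drug before Week 16 for a listed reason and stays in the study;
- one who stops drug for a listed reason but whose study exit is recorded under another heading, such as withdrawn consent or loss to follow-up, both separate lines in Protocol 4.7.

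The estimand makes both non-responders; 6.8.1, read literally, does not. The wording carries more weight because the SAP has moved from the protocol synopsis, which imputes missing values as non-response, to multiple imputation for everyone without an intercurrent event. At stake is whether the primary and key secondary analyses estimate what the SAP declares for these subjects.

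**Working it through.** The plan gives no figure on this point to reproduce. The assumed response rates, power and dropout are not in the public text. The check is therefore a comparison of rules, followed by arithmetic for scale.

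**Step 1. Outcome under each rule** for a subject who stops drug before Week 16 for lack of efficacy, protocol deviation or an adverse event:

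| Status | Estimand (SAP 2.2, 2.4) | SAP 6.8.1 read literally |
|---|---|---|
| Recorded as leaving the study for the same reason | Non-responder | Non-responder |
| Stays in study, Week 16 assessed | Non-responder | Observed response |
| Stays in study, Week 16 missing | Non-responder | Imputed under MAR |
| Study exit coded to another reason, Week 16 missing | Non-responder | Imputed under MAR |

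The rules agree in the first row only. In the last two rows the subject is also left out of the descriptive response percentages, because SAP 6.8.2.1 excludes the MAR group from them. In every discrepant row 6.8.1 gives a response probability of zero or more where the estimand gives exactly zero. Within an arm, the discrepancy can therefore only raise the rate or leave it unchanged.

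**Step 2. Size per subject.** About 240 subjects at 1:1:1:1 (Protocol 4.1) gives 240/4 = 60 per arm.

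- Counted as an observed responder: 1/60 = 1.7 points each.
- Imputed under MAR: k subjects with imputed response probability r add k × r/60. With assumed r of 0.2 to 0.4, one subject adds 0.2/60 = 0.3 to 0.4/60 = 0.7 points. Six subjects add 6 × 0.2/60 = 2.0 to 6 × 0.4/60 = 4.0 points.

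**Step 3. Could it matter to a test?** This is an illustration under assumed counts. It uses an unstratified pooled two-proportion z-test, two-sided, with 60 per arm and 6/60 responders on placebo. It ignores stratification and imputation pooling.

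z = (p₁ − p₀) / √[p̄(1 − p̄) × 2/60]

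At 16/60 on active, p̄ = 22/120 = 0.183 and z = 0.1667/0.0706 = 2.36, so p = 0.018. Recoding active responders to non-response gives:

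| Active responders before recoding | Recoded | p |
|---|---|---|
| 16/60 | 1 | 0.031 |
| 16/60 | 2 | 0.050 |
| 16/60 | 3 | 0.080 |
| 18/60 | 3 | 0.031 |
| 18/60 | 5 | 0.080 |
| 20/60 | 5 | 0.031 |

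A borderline result could move across 0.05 with two or three such subjects. A clearer result would not.

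**Step 4. Do the sensitivity analyses cover it?** In SAP 6.8.2.2:

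- The active-treatment-worst-case analysis sets active subjects with a missing response or an intercurrent event to non-response, so it reaches an off-drug subject whose Week 16 value is missing.
- The tipping-point analysis varies the MAR group from 0% to 100% responders, so it reaches the same subject.
- Neither touches an off-drug subject with an observed Week 16 response, who is neither missing nor, under 6.8.1, an intercurrent-event case.
- The LOCF analysis inherits whichever definition is used.

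**The case against.** The strongest reply is that in this protocol stopping drug usually means leaving the study, so the two definitions pick out nearly the same subjects. Section 4.7 makes an adverse event for which the subject wants to stop treatment a reason for removal. It lists significant protocol violations and unsafe worsening too, and says that subjects whose treatment is interrupted for safety should be withdrawn. The instruction in 6.3 concerns blood sampling and could refer to the four-week follow-up after the last dose. The visible Early Discontinuation and Follow-up procedures (7.1.13, 7.1.15) include no PASI or IGA, and no visible schedule keeps off-drug subjects to Visit 10.

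Much of this stands. It means that few subjects are likely to be affected and that an observed off-drug responder is the rarer case. It does not close the gap. Section 6.3 is operative text and does not limit itself to follow-up. Lack of efficacy short of unsafe worsening has no line of its own in the visible list in 4.7, although a general clause may cover it. The absence of PASI and IGA at early exit also makes the MAR route more likely when the exit reason is coded elsewhere. Because parts of sections 4.7 and 7 are redacted, the documents cannot settle how many subjects could stay on off drug.

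A further reply is that the missing-data route is already stress-tested. That is correct, as Step 4 shows, but sensitivity analyses do not align the primary analysis with its estimand.

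**Conclusion.** The mismatch is real and sits in the rule for the primary and key secondary endpoints. It should be corrected, but it is a narrow defect. Its size is about 1.7 points per subject counted as a responder in an arm of about 60, and less per subject imputed. The number of such subjects is unknown and probably small. The p-values in Step 3 rest on assumed counts.

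A reader might infer more than the documents support:

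- **That any treatment stop is a non-response under the estimand.** It is so only for the three listed reasons.
- **That the error favours the active arms, or those with more adverse-event stops.** The rule also covers stops for lack of efficacy, which could fall more on placebo. The net direction is not shown.
- **That the affected subjects are imputed from on-treatment data.** SAP 6.8.1 describes a model that uses all ITT subjects.
- **That the primary analysis as a whole misses its estimand.** It departs only for the subjects in the discrepant rows of Step 1.

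**What to change.** In SAP 6.8.1, for both endpoints, change the event in the second bullet to *permanently discontinuing study treatment (whether or not the subject remains in the study)*. Keep the same three reasons and the Week 16 limit. The MAR definition and the sensitivity analyses then follow without further edits.

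State how these subjects are identified: last-dose date, action taken for each adverse event, and the End of Study reason. Where the reason for stopping treatment is not recorded directly, assign it at the blinded data review, which SAP 2.2 already uses to determine prohibited medication use.

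The sponsor should also reconcile Protocol 4.7 with 6.3 on whether a subject can remain in the study after permanently stopping drug.

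The SAP change is one phrase and a short derivation note. The cost is some blinded review work. Visible disposition reporting (SAP 6.2) gives reasons for leaving the study only, and the action-taken field covers adverse events but not lack of efficacy or protocol deviation. If the two groups turn out to coincide, no result changes. The change should be made before the Part I analysis, which SAP 7.3 makes final for the primary endpoint.
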